1. INTRODUCTION

This statistical analysis plan (SAP) specifies the statistical methods to be implemented for the analysis of data collected within the scope of Edwards Lifesciences's Protocol, 2020-19 (version F), A randomized trial of the Hypotension Prediction Index in the cardiac operating room and the intensive care unit, provides detailed instructions to study data analysis. If there are conflictions between SAP and other study documents related to data analysis, SAP will be the final document that we will follow.

The primary analyses will be done using SAS, Version 9.4 or later version installed in Edwards Lifesciences' Server. The computation of hypotension duration for each hypotension instance, subject's total hypotension duration, and all other relevant endpoints will be completed with global macro function written with SAS, which is developed and maintained by department of critical care, Edwards Lifesciences.

R will be the support software used in a few applications, such as draw publication quality plots, and application of advanced statistical models in the analysis.

2. STUDY DESIGN

2.1. Study Objectives

The objective of the study is to determine whether the use of the Acumen™ HPI Feature Software to guide hemodynamic management in the cardiac operating room (OR) post-CPB and the cardiovascular intensive care unit (CVICU) reduces the mean duration of hypotension (defined as MAP < 65 mmHg) as compared with the control group. The study is being performed in this patient population to provide information that cannot be readily obtained through additional non-clinical assessments.

2.2. Overall Study Design

This study is a single-center randomized controlled trial to determine whether use of the Acumen HPI Software Feature to guide hemodynamic management in cardiac surgery post-CPB and up to 8-hours post-CPB reduces the amount of hypotension (defined as MAP < 65 mmHg). The results of the HPI arm will be compared with a control group (non-HPI arm). In the control group, the clinician will use non-protocolized standard of care management per clinician and provider judgement.

In accordance with 21 CFR 812.3(m), this trial does not meet the definition of a significant risk investigation for the following reasons:

- The devices in the HPI arm are being studied in accordance with the indications for use and intended use granted by FDA in DEN160044 (March 16, 2018), and therefore are not investigational devices.
- The devices in the treatment group are not implants.

 Edwards	Revision Date: May 7, 2024	Rev	For Use Only by Affiliates of Edwards Lifesciences	Page 6
	Title	A randomized trial of the Hypotension Prediction Index in the cardiac operating room and the intensive care unit		

- The devices in the treatment group do not present a potential for serious risk to the health, safety, or welfare of a subject as only subjects requiring an arterial line will be eligible for enrollment in the trial and the trial relies on the intervention of a learned intermediary prior to initiation of treatment. The devices in the treatment group are of substantial importance in diagnosing, mitigating, or treating disease, or otherwise preventing impairment of human health; however, as described in the de novo classification letter for DEN160044 (March 16, 2018), the Class II (special) controls provide a reasonable assurance of the safety and effectiveness of adjunctive predictive cardiovascular indicators, and specifically, the Acumen™ HPI Software Feature, met the special controls as established by FDA; and the devices in the treatment group are not of substantial importance in curing disease.

Subject participation will include preoperative trial eligibility screening and consent, planned surgical intervention, post-intervention follow-up through discharge, and 30 days post procedure. Discontinued subject data will be analyzed under intent-to-treat and data will be used for safety and performance analyses.

This trial will be conducted in a manner that is consistent with the applicable regulations and in accordance with current Good Clinical Practice (GCP).

2.3. Study Subject Randomization Schema

Subjects will be randomized into two arms, the HPI arm and the non-HPI arm. The randomization will be done automatically by the Electronic Data Capture (EDC) system. To keep the subject balance between HPI arm and control group (1:1), sequentially, 2, or 4, or 6 study subjects passed the qualification screening with yes for all inclusion criteria and no for all exclusion criteria, signed the IFC form, assigned the subject ID, form a subject block. The randomization allocation of study subject will conduct within each block depending on the random number generated from uniform distribution, the block specified cutoff probability will be selected to guarantee half of the subjects will go to the control group and another half will be assigned to the HPI arm. The probability cutoff point to assign a subject to HPI arm or control group will variate among blocks, which is determined by the random seed and the uniform random number produced for each study subject.

Due to system limitations with the electronic data capture (EDC) system, there is a manual process for handling screen failures who are randomized (late screen failures). There is a small chance that some randomization assignments will be skipped due to these screen failures (partially filled blocks), or some randomization assignments given out more than once. These issues may introduce bias in the study. Should these events occur, an additional sensitivity analysis will take place. If randomization assignments are skipped, the study will be assessed to ensure a reasonable balance exists between the cohorts. The collected baseline variables will be compared to ensure that both cohorts are well matched.

 Edwards	Revision Date: May 7, 2024	Rev	For Use Only by Affiliates of Edwards Lifesciences	Page 7
	Title	A randomized trial of the Hypotension Prediction Index in the cardiac operating room and the intensive care unit		

In the event that some of the randomizations are given out twice, a sensitivity analysis will be performed to determine if the duplicate randomization caused any difference in the results. This sensitivity analysis on the primary endpoint will remove all subjects who were included in the duplicate randomization and the results will be compared to the primary endpoint to ensure the results are consistent. If they are consistent between the main analysis and the sensitivity analysis, then it will be determined that there was no bias created. If the results of the sensitivity analysis differ significantly, then both the results for the primary endpoint and the sensitivity analysis will be presented.

2.4. Sample Size Considerations

2.4.1. Hypothesis Test Setting

It is anticipated that the alert function of the Acumen™ HPI Feature Software will reduce the hypotension duration by a clinically relevant amount, which is derived by the consecutive measurements with MAP<65 (mmHg) lasting at least 1 minutes (see appendix). By the HPI CARE study objective, following one-side hypotheses test settings will be designed and applied in sample size estimation and data analysis.

$$H_n: \mu_{HPI} \geq \mu_{ctr}$$

$$H_a: \mu_{HPI} < \mu_{ctr}$$

Here, μ_{HPI}, μ_{ctr} is the mean number of minutes of hypotension duration of HPI arm study subjects and that of control group study subjects respectively.

2.4.2. Experiment Design Parameter

 Edwards	Revision Date: May 7, 2024	Rev	For Use Only by Affiliates of Edwards Lifesciences	Page 8
	Title	A randomized trial of the Hypotension Prediction Index in the cardiac operating room and the intensive care unit		

It is frequently encountered upon intensive care unit (ICU) admission, where patients become hypotensive in the immediate post-operative period, shortly after the arrival from the operating room (OR). Hypotension upon anesthesia-to-ICU drop-off is more frequent than previously reported and may be associated with adverse clinical outcomes^[9]. Many studies have been conducted exploring the risks of intraoperative hypotension during non-cardiac surgery, also there are literatures focusing on the hemodynamic management in operating room during cardiac surgery, but up to now, no valid evidence available from hemodynamic management operation for the patients discharged to ICU could be applied in sample size simulation for HPI CARE study. The association between the severity and duration of intraoperative hypotension and postoperative stroke in patients undergoing cardiac surgery was evaluated in a retrospective cohort study of 7,457 consecutive adult patients who underwent cardiac surgery with the aid of cardiac pulmonary bypass^[9]. From this study, following summary statistics (table 1) are drawn that will be integrated in sample size simulation for HPI CARE study. Recently, a single medical center prospective cohort feasibility clinical study is designed and executed to evaluate the use of the HPI in cardiac surgeries requiring cardiopulmonary bypass (CPB) ^[13]. Totally 37 subjects were enrolled for this study. By 33 valid subjects, the mean total intraoperative hypotension duration is 9 minutes, and the corresponding stand deviation is 15 (minutes) for close chest period in whole cardiac surgery procedure, which will be integrated together with the summary statistics from post cardiac pulmonary bypass (see table 1) in the sample size simulation.

Table 1: Summary Statistics of intraoperative hypotension during post-Cardiac Pulmonary bypass period^[9]

MAP(mmHg)	Stroke (n=111) Mean±STD (minutes)	No Stroke (n=7346) Mean±STD (minutes)	All Patients (n=7457) Mean±STD (minutes)
<55	9.2±20.00	3.8±11.10	3.88±11.30
55-64	23.5±27.30	16.0±18.60	16.11±18.78
<65 (Derived)	32.7±33.84	19.8±21.66	19.99±21.92 *

Note: *The mean and STD of hypotension duration will be used in sample size estimation.

2.4.3. Sample Size Estimate

Because there is no valid evidence available for the hemodynamic management from literature on intensive care unit, in this simulation only the information from closed chest stage and post cardiac pulmonary bypass stage are integrated.

By HPI CARE study objectives, clinical study design, and hypotheses test settings, a one side hypothesis test is the standard method, type I error for this test is 0.025, test power=0.80, control group mean hypotension duration=29 minutes, its stand deviation=29.49, the expected reduction is 30%, by the HPI arm result from non-cardiac clinical study, the ratio between hypotension duration STD and mean is around 1.10. The estimated subjects for each arm by 1:1 allocation is 142 from the simulation completed by SAS PROC POWER. Considered lost follow up, withdraw informed consent form, et al, 10% attrition will put on the estimated sample size. It is 157 subjects for HPI arm and control group.

Variable	Control Group (non-HPI arm)	Test Group (HPI Arm)
----------	--------------------------------	-------------------------

 Edwards	Revision Date: May 7, 2024	Rev	For Use Only by Affiliates of Edwards Lifesciences	Page 9
	Title	A randomized trial of the Hypotension Prediction Index in the cardiac operating room and the intensive care unit		

Mean hypo (minutes)	29 min	20.3 min
SD of Mean hypo minutes	29.49 min	22.33 min
Alpha (overall, one-sided)	0.025	---
Sides	One-Sided	---
Power	0.8	---
Sample size	142	142
Dropout rate	10%	10%
Sample size (subjects)	157	157

3. STUDY ENDPOINTS

3.1. Primary Endpoint

Assessment if the use of the Acumen HPI Feature Software reduces the mean duration of hypotension (defined as MAP < 65mmHg) from the post-bypass period to the first 8-hour ICU period as compared with the control group.

3.2. Primary Safety Endpoint

Serious adverse events through 30 days as indicated below:

- Serious intraoperative and post-operative complications between each cohort
- Device-related serious adverse events (SAEs).

3.3. Secondary Endpoints

The following secondary endpoints will be analyzed:

- Additional definitions of hypotension:
 - Time Weighted Average (TWA) of MAP < 65 mmHg in the OR Period (T1)
 - TWA of MAP<65 mmHg in the CVICU Period (T2)
 - TWA of MAP < 65 mmHg in the CVICU Period, pre extubation (T3)
 - TWA of MAP < 65 mmHg in the CVICU Period, post extubation (T4)
 - Mean duration in minutes of MAP < 65 mmHg in the time periods of T1, T2, T3 and T4
 - Mean duration in minutes of MAP < 60 mmHg in the time periods of T1, T2, T3 and T4
 - Mean duration in minutes of MAP < 55 mmHg in the time periods of T1, T2, T3 and T4
 - Mean duration in minutes of MAP < 50 mmHg in the time periods of T1, T2, T3 and T4
- Clinical endpoints:
 - Acute kidney injury (AKI)⁷, as defined by the modified KDIGO criteria, stages 1, 2 and 3
 - Neurocognitive deficit, as evaluated by the MMSE, CAM-ICU⁷, and bCAM assessments. [bCAM will be used for delirium screening for patients who are deemed ready for transfer to the floor per ICU attending team's assessment, even if they are physically in the ICU]
 - Periprocedural Myocardial injury, measured with high-sensitivity Troponin I and defined by a threshold of 70 times the upper reference limit⁶. or >1400 pg/ml

 Edwards	Revision Date: May 7, 2024	Rev	For Use Only by Affiliates of Edwards Lifesciences	Page 10
	Title	A randomized trial of the Hypotension Prediction Index in the cardiac operating room and the intensive care unit		

3.4. Exploratory Endpoints

The exploratory evaluations are indicated below:

- Subgroup analysis of primary and secondary endpoints by age stratification
- Subgroup analysis of primary and secondary endpoints by gender
- Subgroup analysis of primary and secondary endpoints by race
- Protocol adherence to HPI alert, as defined as by >50% HPI alerts responded to with HPI suggested interventions with documented intervention per the suggested treatment algorithm within a 5-minute timeframe.
- Difference in time spent in hypertension defined as Time weighted average (TWA)TWA of MAP>110, >120 and >130 mmHg post-cardiopulmonary bypass CPB) through the first 8-hour ICU period as compared with the control group.
- In-hospital mortality rate
- Incidence of cerebral desaturations defined as total time below 10% relative to baseline NIRS values.
- Percent of monitoring time with CO or CI within 10% relative to pre-induction baseline
- ICU Length of Stay
- Hospital Length of Stay
- Time to extubation
- New onset atrial fibrillation, detected prior to ICU discharge

 Edwards	Revision Date: May 7, 2024	Rev	For Use Only by Affiliates of Edwards Lifesciences	Page 11
	Title	A randomized trial of the Hypotension Prediction Index in the cardiac operating room and the intensive care unit		

4. ANALYSIS POPULATIONS

A subject will be considered enrolled in the trial once the subject has signed the informed consent, has been assigned a Study Identification Number (Study ID), an arterial line has been placed and Acumen IQ has been connected. The Study ID will be an 874-XXX (6-digit) number; the first three numbers will identify the site, and the second set of numbers will identify the subject identification number. Roll-in cases will be assigned a unique Study ID and be analyzed separately from the pivotal cohort. There will be an identification number assigned to each investigator. The ID for each subject will remain the same throughout enrollment at each site.

4.1. Modified ITT (mITT) Population

The mITT population is composed of all subjects who pass the screen (inclusion/exclusion) evaluation, sign the informed consent form (ICF), are assigned a subject ID, and are randomized to a study group, an arterial line has been placed and the FloTrac or Acumen IQ Sensor has been connected.

4.2. Full Analysis Set (FAS) Population

The FAS population is a subset of the mITT population and will consist of all enrolled pivotal subjects who undergo cardiac surgery ≥ 2 hours duration with the aid of cardiopulmonary bypass, have one postoperative assessment, and have valid hemodynamic observations.

4.3. Per Protocol (PP) Population

The per protocol (PP) population is a subset of the subjects in the FAS who are more compliant with the protocol and is characterized by criteria such as the following: i) the completion of a certain pre-specified minimal exposure to the treatment regimen; ii) the availability of measurements of the primary endpoint(s); iii) the absence of any major protocol violations including the violation of entry criteria.

4.4. Complete Case (CC) Population

The CC population is composed of all the pivotal subjects who complete surgery and complete the trial.

4.5. Roll-in Subjects

To prevent a learning curve bias, up to five (5) roll-in cases may be performed at the site, as needed. Roll-in cases will be analyzed separately from the pivotal cohort.

4.6. Screen Failure

Screen failures are defined as subjects who consent to participate in the clinical trial but who are not randomly assigned to a trial arm. Screen failures will be represented in subject accountability table by counts and percentages. Screen failures also includes study subjects who were included in the study but did not meet all the inclusion criteria.

5. DEFINITIONS

 Edwards	Revision Date: May 7, 2024	Rev	For Use Only by Affiliates of Edwards Lifesciences	Page 12
	Title	A randomized trial of the Hypotension Prediction Index in the cardiac operating room and the intensive care unit		

5.1. Analysis Dates and Days

Reference Start Date (Day 0)

On the day of the surgery, the start of the study is defined as when the arterial line has been connected and after initial stabilization (max 15 minutes). The date of the surgery will be used as the reference start date (day 0).

If a subject has multiple procedure forms, we will present information on the procedure with the earliest date where the site has indicated that the arterial line was placed.

If no form has this indicated, then the procedure information corresponding to the procedure with the earliest date that indicated an arterial line was placed will be used. If no form has this listed, then the date of the earliest procedure will be used.

Last Participation Date

The Last Participation Date is defined as the last date recorded. This will be the study exit date if the subject has exited the study or the latest date the subject was known to be alive and on study.

Treatment Start Date

The Treatment Start Date is defined as the date of the surgery.

Study Day

Study Day = Date – Reference Start Date

Last Participation Day

Last Participation Day = Last Participation Date – Reference Start Date

Note: Last Participation Day is used as the censor day for any survival analysis.

5.2. Analysis Windows

No analysis windows will be used for this study. If some visits are far outside of the time, then a sensitivity analysis that removes the out of window visits may be performed to assess the impact of the out of window visits.

6. DATA AND ANALYSIS CONVENTIONS

6.1. General Conventions

The baseline characteristics and demographics of each study subject will be collected during the subject

 Edwards	Revision Date: May 7, 2024	Rev	For Use Only by Affiliates of Edwards Lifesciences	Page 13
	Title	A randomized trial of the Hypotension Prediction Index in the cardiac operating room and the intensive care unit		

screening process.

Descriptive summaries will follow the conventions below:

- For continuous variables, summary statistics will include sample size, mean, median, standard deviation (SD), and/or standard error (SE), Q1, Q3, minimum, and maximum.
- For categorical (including ordinal) variables, summaries will include the count and percentage of subjects in each category.
- Time-to-event variable summaries will include the number of subjects with the event and Kaplan-Meier estimates at given time points. Standard errors will be calculated using Greenwood's formula.

All analyses will be performed using SAS® Software version 9.4 or later (SAS Institute, Inc., Cary, NC) unless otherwise specified.

6.2. Handling of Missing Data

Demographic and baseline characteristics are collected from the study subjects as part of screening. If missing data are not related to the subject's eligibility criteria, missing data will be presented by the valid sample size in the demographic and baseline characteristics summary statistics table. Subjects with missing data will be included in the final analysis. However, if the missing data are related to the subject's eligibility, this will be considered a protocol deviation, and in this case, the study data from this subject will be reviewed internally, to determine if the subject should be excluded from the final analysis set.

Algorithms for imputing the missing dates of safety events are given below. Generally, the safety event date will be assigned as the earliest possible date that is on or after the procedure date.

- If the year is unknown, then the date will be imputed using the procedure date
- If the month is unknown, then:
 - If the year matches the year of the procedure date, then impute the month and day using the procedure date
 - Otherwise, assign the procedure month
- If the day is unknown, then:
 - If the month and year match the month and year of the procedure date, then impute the day using the procedure date
 - Otherwise, assign '01'

Unless otherwise noted, no other data imputation will be made.

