Subjects will be randomized into two arms, the HPI arm and the non-HPI arm. The randomization will be done automatically by the Electronic Data Capture (EDC) system. The subject will be blinded. Due to the nature of the interventions, the investigators and treating anesthesiologist, anesthesia nurse, intensivist and critical care nurse will not be masked to group allocation.

The HPI arm will utilize the HemoSphere Advanced Monitoring Platform with the Acumen™ HPI Software Feature. The treating cardiac anesthesiologist/anesthesia nurse in the operating room and the critical care

THIS DOCUMENT CONTAINS CONFIDENTIAL AND PROPRIETARY INFORMATION OF EDWARDS LIFESCIENCES, LLC. IT MAY NOT BE REPRODUCED OR DISCLOSED WITHOUT PRIOR WRITTEN PERMISSION FROM EDWARDS LIFESCIENCES, LLC.

Edwards Lifesciences, Edwards, the stylized E logo, HemoSphere, Acumen IQ, Swan Ganz and ForeSight Elite are trademarks of Edwards Lifesciences Corporation.

nurses/intensivists/advance practice providers in the ICU will be trained to understand Acumen™ HPI Software Feature and the advanced hemodynamic parameters provided. The treating anesthesiologist, anesthesia nurse, intensivist, and critical care nurse will be provided with guidance by means of a flowchart suggesting what to treat and what the cause of hypotension is (see Figure 3. HPI Arm Protocol). Timing of treatment and choice of treatment is then left to the discretion of the attending intensivist and critical care nurse.

In the non-HPI arm, clinicians will be using non-protocolized standard of care to treat subjects.

[figure not shown]

Figure 3. HPI Arm Protocol

Note: Clinicians should validate the appropriateness of protocol recommendations, and provide treatment based upon their clinical judgment.

Schema

Screening and consenting subjects will occur during the pre-anesthesia visit. Once the subject is consented, the subject will undergo a Mini-Mental State Examination (MMSE).

After the subject has consented and prior to surgery, the subject will be randomized into the HPI arm or the non-HPI arm (control group). The randomization assignment must not be revealed to the clinicians until surgery. If a clinician randomizes the subject, they must not be involved in the care of the subject in the OR. A clinical research coordinator or a designee who is delegated to consent and/or randomize the

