16. DATA COLLECTION METHODS

Trial data will be captured utilizing electronic Source (eSource) and electronic Case Report Forms (eCRFs) including the 30-day follow-up as well as downloaded files captured directly via the use of the HemoSphere advanced monitor. Data collected from the HemoSphere advanced monitor will be downloaded at the end of each procedure and stored on a USB stick. USBs will be stored in a secure location at the site, accessible only to Trial site personnel. The HemoSphere data on USBs may be shipped to the Sponsor at any point in time of the Trial per the request of the Sponsor.

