8. STATISTICAL ANALYSIS OF STUDY ENDPOINTS

8.1. Primary Effectiveness Endpoint

Primary objective of this clinical study is to determine whether the use of the Acumen™ HPI Feature Software to guide hemodynamic management in patients undergoing cardiac surgery requiring cardiopulmonary bypass reduces the mean duration of hypotension (defined as MAP < 65 mmHg) from the post-bypass period in the cardiac operation room (OR) and the cardiovascular intensive care unit (CVICU). With MAP measurements sampled during post-CPB and up to first 8 hour in ICU, downloaded from the advanced hemodynamic monitoring platform, the primary effectiveness endpoint the hypotension duration of study subject is calculated with the algorithm illustrated in sample size estimation section 2.4.3.

The primary effectiveness endpoint will be analyzed on the FAS population.

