8.1.3. Sensitivity Analysis

The objective of sensitivity analysis is to guarantee the robustness of the statistical analysis conclusion drawn from statistical hypothesis test. Following sensitivity analyses are designed in this study:

- A. Modification of hypotension definition:
 - A1. The effectiveness of the threshold of MAP on statistical conclusion, check the analytical conclusion sensitivity to changes of the MAP threshold value to define hypotension instance from 50 mmHg to 70 mmHg with step=5 mmHg.
 - A2. The time length cut off used in hypotension instance definition, check the analytical conclusion sensitivity to changes of the cut off time length from 20 seconds to 80 seconds with step=20 seconds.
- B. The effectiveness of sample size:
 - B1. With bootstrap method, draw analytical conclusion by analysis based on the sub-set of study data sampled from the whole study data, check the consistency between the whole data analysis result and the simulated sub-dataset analysis result.
 - B2. Including the study subject with missing covariate information or cohort structure in the analytical dataset, check the consistency between the analysis with all study subject and on the analysis result with FAS subject.

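### SAP 6.2 lets internal reviewers use a subject's study data to decide whether missing eligibility data should remove that subject from the final analysis set, with no criterion, masking or deadline

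*Combined protocol and SAP*

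**What the plan says.** SAP 6.2 separates two kinds of missing baseline data. Subjects whose missing items have no bearing on eligibility stay in the final analysis. For the others, "if the missing data are related to the subject's eligibility, this will be considered a protocol deviation", and then "the study data from this subject will be reviewed internally, to determine if the subject should be excluded from the final analysis set".

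The related provisions are:

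- **Primary set (SAP 8.1).** "The primary effectiveness endpoint will be analyzed on the FAS population".
- **FAS (SAP 4.2).** A subset of the mITT: pivotal subjects with on-pump surgery of at least 2 hours who "have one postoperative assessment, and have valid hemodynamic observations". It has no rule for missing eligibility data.
- **mITT (SAP 4.1).** Begins with "all subjects who pass the screen (inclusion/exclusion) evaluation".
- **Per-protocol set (SAP 4.3).** A subset of the FAS that already removes subjects who violate entry criteria.
- **Masking (protocol section 4, Randomization and Blinding).** The subject is blinded. Investigators and treating staff "will not be masked to group allocation". Sponsor personnel are not mentioned.
- **Data flow (protocol section 16).** "The HemoSphere data on USBs may be shipped to the Sponsor at any point in time of the Trial", on the sponsor's request.
- **Sensitivity analysis B2 (SAP 8.1.3).** "Including the study subject with missing covariate information or cohort structure in the analytical dataset", compared with the FAS result.

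**The concern.** Who belongs to the primary analysis set should be settled by rules that cannot depend on assigned arm or observed outcome. SAP 6.2 sets up a case-by-case decision and names the subject's study data as the material to be reviewed. Read literally, that includes the HemoSphere pressure record from which hypotension minutes are computed, and the treatment assignment.

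If a reviewer can see either, keeping or dropping a subject can shift the difference between arms, even when each decision looks reasonable alone. What is at stake is the type I error of the primary test, and whether the sponsor could later show that exclusions were made blind to the result.

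**Working it through.** **Step 1: trace the rule to the primary test.** The final analysis set is not a defined term. SAP 4 defines the mITT, FAS, PP and CC sets. The primary test uses the FAS, so the FAS is the natural reading, but this is an inference. SAP 1 states that the SAP prevails over other study documents on analysis matters, so the protocol cannot supply the missing limits.

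**Step 2: look for a safeguard elsewhere.**

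- SAP 4.1 and 4.2 give no objective rule for missing eligibility items.
- The intent-to-treat sentence in SAP 2.2 concerns discontinued subjects only.
- SAP 8.1.4 has the study team act on a comparative interim result. Nothing requires exclusion decisions to precede that look.
- Sensitivity analysis B2 does not name missing eligibility data, and it leaves the primary set as the reviewers made it.

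No section supplies a criterion, masking, a restriction to eligibility records or a deadline.

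**Step 3: reproduce the design figure.** Inputs from SAP 2.4.3 are control mean 29 and SD 29.49; HPI mean 29 × 0.70 = 20.3 and SD 1.10 × 20.3 = 22.33; difference 8.7; one-sided alpha 0.025; power 0.80.

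n per arm = (1.960 + 0.842)² × (29.49² + 22.33²) / 8.7² = 7.85 × 1368.3 / 75.69 ≈ 142.

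This matches the SAP. The Pocock allowance gives 142 × 1.11 = 157.6, or 158 evaluable per arm, and 157.6 / 0.9 = 175.1 matches the planned 175.

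**Step 4: bound the effect.** The documents give no rate of missing eligibility data, so the rate is an assumption and a range is shown. Simulation assumptions:

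- no treatment effect, with gamma-distributed durations of mean 29 and SD 29.49 in both arms;
- 158 per arm, with missingness independent of outcome;
- the pooled one-sided t-test, treated as one look;
- 40,000 trials per setting. The simulation standard error near 0.025 is √(0.025 × 0.975 / 40,000) ≈ 0.0008, and repeat runs agreed within about 0.003.

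In the adverse rule, every flagged HPI subject above 29 minutes and every flagged control below 29 minutes is dropped.

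| Missing rate | Flagged per arm (rate × 158) | Both arms, level 0.025 | HPI arm only, level 0.025 | Both arms, level 0.0154 |
|---|---|---|---|---|
| 2% | 3.2 | 0.033 | 0.029 | 0.021 |
| 5% | 7.9 | 0.051 | 0.036 | 0.034 |
| 10% | 15.8 | 0.099 | 0.052 | 0.069 |

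The spurious benefit under two-arm selection is about 1.1 minutes at 5% and 2.3 minutes at 10%. At 1% missing the two-arm error is about 0.03; at 0.5%, less than one subject per arm, it is about 0.027.

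**Step 5: control condition.** If every flagged subject is kept, or every flagged subject is dropped without looking, the error stays near 0.025. The inflation comes from outcome-informed choice, not from missing data or smaller numbers.

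**The case against.** Four arguments on the other side carry weight.

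**The rule may rarely be used.** SAP 2.3 admits subjects to a randomisation block only after they have met every inclusion criterion and no exclusion criterion. Protocol section 19 has missing eCRF data queried throughout. Deviations are recorded, and an accountability table and CONSORT diagram are planned, so exclusions would be visible. This stands, and it is why the size is probably small. Visibility does not show how each decision was made.

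**Some eligibility facts are intraoperative.** A reader might infer that every eligibility gap predates randomisation, so that nothing recorded later could bear on it. The documents do not support that. Randomisation precedes surgery, but exclusion 5 includes pre-pump and post-pump LVEF, exclusion 9 allows a sustained Swan-Ganz reading before bypass, and exclusion 10 is a return to bypass. Reviewers may properly need intraoperative eligibility records. They do not need hypotension minutes or arm.

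**The text does not say that reviewers see arm or outcome.** A reader might infer an unmasked sponsor. The protocol names investigators and treating staff as unmasked and is silent on sponsor reviewers. It permits shipment of monitor files without linking them to this review. Study data may have been meant as eligibility records only. What stands is that masking and scope are unspecified.

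**The simulated rule amounts to deliberate manipulation.** It does, so its results are ceilings. A reader might infer that even well-meant decisions would favour the HPI arm; nothing in the documents shows such a tendency.

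**Conclusion.** The point holds as a gap in an operative rule. SAP 6.2, followed as written, allows exclusion from what is most naturally the primary analysis set after a review of study data, with no criterion, masking, restriction or deadline. It permits arm- or outcome-dependent exclusion; it does not show that this will happen.

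The actual effect cannot be estimated because the documents give no missing rate. The ceiling depends on the assumed rate, gamma-distributed durations, no true effect and fully adverse choices. Under those assumptions it runs from about 0.03 at 2% missing to 0.10 at 10% against a nominal 0.025, or from about 0.02 to 0.07 against 0.0154. Both sets treat the test as a single look and do not describe the trial's overall two-look error. It would go too far to infer that the primary result will be biased or could not be defended. The change is worth making because the gap is plain in the text and cheap to close.

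**What to change.** Replace the exclusion sentence in SAP 6.2 with wording such as:

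> A missing eligibility item is recorded as a protocol deviation and does not by itself remove a randomised subject from the mITT or FAS. Such subjects may be excluded from the PP set only, using eligibility source documents alone (including intraoperative eligibility records for exclusions 5, 9 and 10), by reviewers without access to arm or hypotension-duration data. Decisions are logged before the interim analysis for subjects included in it, and before database lock for all others.

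Two other sections must be reconciled with this. SAP 4.1 requires a passed screening evaluation for the mITT, so it should say how a subject with an unverified item is counted. SAP 4.6 counts included subjects who did not meet all inclusion criteria as screen failures, so it should say that a missing item alone does not have that effect.

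The cost is one replaced paragraph and two short edits, with no change to the sample size. The downside is that a few possibly ineligible subjects remain in the primary set; the PP analysis would show their influence.
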